7.3.3. DF/HCC Adverse Event Reporting Guidelines

Investigative sites within DF/HCC will report AEs directly to the DFCI Office for Human Research Studies (OHRS) per the DFCI IRB reporting policy.

7.3.4. Protocol-Specific Adverse Event Reporting Exclusions

For this protocol only, the AEs/grades listed below do not require expedited reporting to the Overall PI or the DFCI IRB. However, they still must be reported through the routine reporting mechanism (i.e., case report form).

CTCAE SOC	Adverse Event	Grade	Hospitalization/ Prolongation of Hospitalization	Attribution	Comments
Allergic Reaction		1,2			
Alanine aminotransferase increased		1, 2			
Aspartate aminotransferase increased		1, 2			
Ataxia		1, 2			
Cognitive disturbance		1			
Dizziness		1, 2			
Lethargy		1			
Agitation		1, 2			
Confusion		1			
Depression		1, 2			

7.4. **Reporting to the Food and Drug Administration (FDA)**

Not applicable since FDA deemed this IND exempt.

7.5. **Reporting to Hospital Risk Management**

Participating investigators will report to their local Risk Management office any participant safety reports, sentinel events or unanticipated problems that require reporting per institutional policy.

7.6. **Routine Adverse Event Reporting**

All Adverse Events **must** be reported in routine study data submissions to the Overall PI on the toxicity case report forms. **AEs reported through expedited processes (e.g., reported to the IRB, FDA, etc.) must also be reported in routine study data submissions.**

8. PHARMACEUTICAL INFORMATION

A list of the adverse events and potential risks associated with the investigational or other agents administered in this study can be found in Section 7.1.

8.1. Cannabidiol (Epidiolex)

8.1.1. Description

Cannabidiol (Epidiolex) is an herbal-derived phytocannabinoid. The molecular formula is $C_{21}H_{30}O_2$. The molecular weight is 314.46. After oral administration, the time to maximum concentration (Cmax) is 2.5-5 hours. In individuals who have recently ingested a high fat diet, the Cmax increases by 5-fold. Cannabidiol is protein-bound but has a volume of distribution of 20963-32849L. After twice daily dosing, the half-life of cannabidiol is 56-61 hours. Cannabidiol is hepatically metabolized via CYP2C19 and 3A4 to 7-OH-CBD. 7-OH-CBD is the major metabolite and remains pharmacologically active. Metabolites of cannabidiol undergo fecal-elimination. A secondary route of elimination is renal. Cannabidiol is a substrate for CYP 2C19 and 3A4 and inhibitor of 1A2 and 2B6. A minor metabolite, 7-COOH-CBD is a PgP substrate. Major drug interactions include concomitant use of clobazam and valproic acid.

Coadministration of clobazam with CBD results in increased 7-OH-CBD levels.

Coadministration of valproic acid with CBD has no effect on valproate levels, but the combination may result in reversible hepatic injury.

8.1.2. Form

Cannabidiol (Epidiolex), manufactured by GW Pharmaceuticals, is a clear (colorless to yellow) solution intended for oral consumption. In addition to CBD (100 mg/mL), it contains sesame seed oil, sucralose, alcohol and strawberry flavor.

8.1.3. Storage and Stability

Cannabidiol (Epidiolex) should be stored at room temperature 20 to 25°C (68 to 77 °F) in its original bottle and in an upright position. Excursions are permitted between 15 to 30°C (59 to 86°F). Once opened, Cannabidiol has a shelf life of 84 days. The oral solution may be kept in the syringe for up to 24 hours. For this reason the medication will be overnighted to patients.

8.1.4. Compatibility

Not Applicable

8.1.5. Handling

This is commercially available and no special handling considerations are necessary.

8.1.6. Availability

Cannabidiol (Epidiolex) is commercially available and the DFCI pharmacy will purchase the drug on behalf of our research team. The study will cover the cost for Epidiolex.

8.1.7. Preparation

Cannabidiol (Epidiolex) at the appropriate dose will be loaded into syringe labeled “Cannabidiol or Placebo” (or something similar).

8.1.8. Administration

Disposable 10mL oral syringe will be used to administer cannabidiol (Epidiolex) PO at the conclusion of Timepoint 1.

8.1.9. Ordering

Cannabidiol (Epidiolex), which is commercially available, will be obtained through GW Pharmaceuticals. The study drug will be shipped to and logged at the investigational pharmacy at DFCI. The research pharmacy will dispense the study drug either directly to the participant or to the study staff for mailing. Patient drug accountability will be ensured through self-report in the form of query on Study Day Timepoint 2 (Appendix H).

8.1.10. Accountability

The investigator, or a responsible party designated by the investigator, will maintain a careful record of the inventory and disposition of the agent using the NCI Drug Accountability Record Form (DARF) or another comparable drug accountability form. (See the NCI Investigator’s Handbook for Procedures for Drug Accountability and Storage.)

8.1.11. Destruction and Return

Expired or unused supplies of cannabidiol or placebo will be destroyed according to institutional guidelines. Destruction will be documented in the Drug Accountability Record Form. If the study drug is in possession of the study participant and they are unable to take the drug during the time period. We will ask the participant to return the unused investigational drug for destruction and log this on our internal drug tracking log.

8.2. Placebo

8.2.1. Description

The Dana-Farber Research Pharmacy will create the placebo as follows: a non-sterile formula of Karo Light Corn Syrup and FLAVORx strawberry cream flavoring in a ratio 20 ml:7 drops. Karo Light Syrup consists of salt, vanilla extract (vanilla beans, water, ethyl alcohol).

8.2.2. Form

Formulated by the Dana-Farber Research Pharmacy, the placebo is a non-sterile, caramel-colored solution intended for oral consumption, containing Karo Light Corn Syrup and FLAVORx strawberry cream flavoring in a ratio 20 mL:7 drops. The strawberry cream flavoring is dye-free and safe for the following allergies: milk, egg, soybeans, peanuts, tree nuts, wheat, grain, fish, shellfish, seeds, latex and some dyes.

8.2.3. Storage and Stability

Placebo should be stored at room temperature (68 to 77 F) in a bottle kept in an upright position. FLAVORx has an expiry date on the stock bottle. The oral solution may be kept in the syringe for up to 24 hours. For this reason the medication will be overnighted to patients.

8.2.4. Compatibility

Not applicable

8.2.5. Handling

No special handling considerations are necessary.

8.2.6. Availability

The Dana-Farber Research Pharmacy will purchase the components of the placebo, which are commercially available, on behalf of our research team. The study will cover the cost for placebo.

8.2.7. Preparation

An appropriate dose of the placebo will be loaded into syringe labeled “Cannabidiol or Placebo” (or something similar).

8.2.8. Administration

Disposable 10mL oral syringe will be used for patients to self-administer placebo PO.

8.2.9. Ordering

Components of the placebo are commercially available, and various manufacturers may be used to purchase the product by Dana-Farber Research Pharmacy. The components of the placebo will be logged at the investigational pharmacy at DFCI. The research pharmacy will dispense the placebo either directly to the participant or to the study staff for mailing. Patient drug accountability will be ensured through self-report in the form of query on Study Day Timepoint 2 (Appendix H).

8.2.10. Accountability

The investigator, or a responsible party designated by the investigator, will maintain a careful record of the inventory and disposition of the agent using the NCI Drug Accountability Record Form (DARF) or another comparable drug accountability form. (See the NCI Investigator's Handbook for Procedures for Drug Accountability and Storage.)

8.2.11. Destruction and Return

Expired or unused supplies of cannabidiol or placebo will be destroyed according to institutional guidelines. Destruction will be documented in the Drug Accountability Record Form.

9. STUDY CALENDAR

	Baseline assessment	Timepoint 1 Treatment day, pre-assessment	Timepoint 2 Treatment day, post-assessment	Timepoint 3 Follow-up assessment
	Prior to Timepoint 1	Within 48 hours of a CT/PET scan to assess tumor burden	3 (+/- 1) hour post ingestion	<1-week (+/- 7 days) post ingestion
Background Information				
Informed consent***	X			
Screener questionnaire	X			
Demographics	X			
Medical history	X			X
Concurrent medications	X	X		
Performance status	X			
LFTs	X			
bHCG**	X			
GAD-7	X	X		
PHQ9	X	X		
Cannabis History Questionnaire	X			
Cannabidiol (Epidiolex) vs. Placebo		X*		
Confirmation of study drug consumption				
Patient Provisions				
\$50 gift card				X
Primary endpoints				
VAMS afraid subscale		X	X	
Secondary endpoints				
NPRS	X	X	X	
EORTC-QLC30-nausea		X	X	
Other subscales of VAMS		X	X	
Qualitative interview				X
Safety Monitoring				
Adverse Event Evaluation		X	X	

* = Study drug to be administered after completion of Treatment day, pre-assessments

**= bHCGs will be collected on all potential participants under the age of 54-years, unless known to be post-menopausal or status post hysterectomy

*** = to be completed with physician involvement

10. DATA REPORTING / REGULATORY REQUIREMENTS

Adverse event lists, guidelines, and instructions for AE reporting can be found in Section 7.0 (Adverse Events: List and Reporting Requirements).

10.1. Data Reporting

10.1.1. Method

The study staff will collect, manage, and perform quality checks on the data for this study. This study will be monitored by the Clinical Data Update System (CDUS) Version 3.0. Cumulative protocol- and participant-specific CDUS data will be submitted electronically to CTEP on a quarterly basis, either by FTP burst of data or via the CDS web application. Reports are due January 31, April 30, July 31, and October 31. Instructions for submitting data using the CDUS can be found on the CTEP Web site (<http://ctep.cancer.gov/reporting/cdus.html>).

10.1.2. Responsibility for Data Submission

Participant institutions are responsible for submitting CDUS data and/or data forms to either the Coordinating Center or to the Lead Organization on the study quarterly. The date for submission to the Coordinating Center or to the Lead Organization will be set by them. CDUS does not accept data submissions from the participant institutions on the study. When setting the dates, allow time for Coordinating Center compilation, Overall PI review, and timely submission to CTEP by the quarterly deadlines (see Section 12.1.1). For trials monitored by CTMS, a quarterly report of data will be provided by Theradex to the Coordinating Center.

Either the Coordinating Center or the Lead Organization is responsible for compiling and submitting CDUS data to CTEP for all participant institutions and for providing the data to the Overall PI for review.

10.2. Data Safety Monitoring

The DF/HCC Data and Safety Monitoring Board (DSMB) will review and monitor study progress, toxicity, safety and other data from this study. The Board is chaired by a medical oncologist from outside of DF/HCC and its membership composed of internal and external institutional representation. Information that raises any questions about participant safety or protocol performance will be addressed by the Overall PI, statistician and study team. Should any major concerns arise, the DSMB will offer recommendations regarding whether or not to suspend the study.

The DSMB will meet twice a year to review accrual, toxicity, response and reporting information. Information to be provided to the DSMB may include: participant accrual; treatment regimen information; adverse events and serious adverse events reported by category; summary of any deaths on study; audit results; and a summary provided by the study team. Other information (e.g. scans, laboratory values) will be provided upon request.

11. STATISTICAL CONSIDERATIONS

This is a phase II, randomized, placebo-controlled study to assess the preliminary efficacy of offering a single dose of CBD versus placebo in reduction of anxiety in patients with advanced (stage IV) solid tumor anticipating CT to assess tumor burden. Eligible patients must have measurable anxiety-- at least “mild” anxiety as measured by the GAD-- at the pre-screen visit.

Anxiety level at each of the time points (pre-screening visit, pre-dose, and 3[+/-1] hour post dose) will be plotted for each study group. The paired change (pre-dose to post-dose) in anxiety will be estimated along with a 95% confidence interval for each study group. The change in anxiety will be compared by study group with a Wilcoxon rank sum test. The side-effect profile, as measured by the PRO-CTCAE will be tabled according to side effect. Patient reported experience with CBD and the acceptability will be summarized with descriptive statistics and qualitative methodology as appropriate

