1.2 Secondary Objectives

To assess, using the Patient-Reported Outcomes version of the Common Terminology Criteria for Adverse Events (PRO-CTCAE™) and a qualitative assessment, patient-reported side effects and acceptability of taking oral CBD (versus placebo) for managing anticipatory anxiety.

To evaluate whether CBD is superior to placebo in improving mood (as measured by VAMS subscales), nausea (as measured by the European Organisation for Research and Treatment of Cancer core quality of life questionnaire-nausea subscale) and pain levels (as measured by the Numeric Pain Rating Scale [NPRS]) 3(+/-1) hours after study agent administration in patients with advanced cancer.

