Timepoint 1 (Pre-drug Administration): Regardless of randomization arm, all participants will complete a set of questionnaires. The study team will review questionnaire responses assessing cannabis and benzodiazepine uses (e.g. section 3.1.8 & 3.1.9 of the eligibility criteria). If a participant indicates they have consumed either within the prohibited timeframe, the study team will attempt to delay study drug administration in order to meet eligibility criteria. (Section 5 offers full details on consuming study drug). However, if the study drug administration cannot be delayed, the Treatment Day will be rescheduled to coincide with the next scheduled CT scan or positron emission tomography (PET). See section 8.1.11. for unused study drug destruction.

Timepoint 2 (Post-drug Administration): All participants will complete a set of questionnaires.

Timepoint 3: Study staff will phone the participant within a week +/- 7 days of study drug consumption to conduct a brief, semi-structured audio-recorded interview.

At study completion participants will receive a \$50 gift card. They will also receive up to \$50 for qualifying study-related travel costs and/or expenses. After all study procedures are completed, the research team will contact participants to inform of which arm they were assigned after unblinding and share any publications that come from this study.

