5.1.3 Instruments measuring study outcomes:

Demographic questionnaire (Baseline):

Variables of interest will be obtained via self-report and include: age, ethnicity, race, marital status, education, and occupational status.

Cannabis History Questionnaire (Baseline):

Cannabis use history will be obtained via self-report.

Generalized Anxiety Disorder- 7 (GAD-7) (Baseline, Timepoint 1): The widely used and validated GAD-7 measures anxiety severity on a 4-point Likert-type scale from not at all to

nearly every day. The presence of baseline anxiety, as measure by a GAD-7 score >4 , is necessary for inclusion in this study.

Patient Health Questionnaire (PHQ-9) (Baseline, Timepoint 1): The widely used and validated PHQ-9 is a 9-item depression severity measure, with scores ranging from 0 to 27. Patients are asked to rate how they felt over the past two weeks using a 4-point Likert scale. Given that anxiety and depression are closely intertwined, this measure will help us to demonstrate that the active drug and placebo arms manifest similar levels of dysphoric distress. This measure will also help in screening to rule out “uncontrolled mental illness.”

VAMS (Timepoint 1, and Timepoint 2): The Visual Analog Mood Scale (VAMS) a validated in-the-moment measure of eight specific mood states: Afraid, Confused, Sad, Angry, Energetic, Tired, Happy, and Tense. Each scale consists of a 100 mm vertical line connecting a neutral face and a face displaying a particular mood state (with an accompanying descriptor). Subjects are asked to mark their mood along this continuum. The measure is scored using a metric ruler and the “Afraid” subscale will serve as our primary endpoint. Other subscales will serve as exploratory endpoints.

EORTC-QLQc30-nausea (Timepoint 1, and Timepoint 2): The EORTC-QLQc30-nausea is a widely used and validated measure of symptom burden. It consists of 30-items, the first 28 of which employ a four-point scale (the final two are measured along a seven-point scale). Single item measures range in score from 0 to 100, with higher scores representing lower symptom burden. For the purposes of this study we will administer two items from the EORTC-QLQc30 on nausea and vomiting to assess a secondary endpoint.

Numeric Pain Rating Scale (Baseline, Timepoint 1, Timepoint 2): This widely used in-the-moment pain intensity scale is scored from 0 to 10 (with 10 representing “worst possible” pain). The NPRS will again help us to assess secondary endpoints.

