Medical Record Review (Baseline, Timepoint 3): A member of the study team will record clinical data, including cancer diagnosis, disease stage, histology, and cancer treatments. Comorbidities or current medical history will also be extracted from medical records.

5.2.Pre-Treatment Criteria

5.2.1. Participants must have normal hepatic function at baseline as outlined below:

- total bilirubin	≤ 2 times institutional upper limit of normal (ULN)
- AST(SGOT)/ALT(SGPT)	$\leq 3 \times$ institutional ULN
- GAD-7 ≥ 5	

5.2.2. Cycle 1, Day 1

- Karnofsky $\geq 60\%$.

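### PRO-CTCAE is the named measure for the side-effect objective but is in neither the instrument list nor the calendar, and no structured adverse-event question is scheduled after Timepoint 2

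*Combined protocol and SAP*

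**What the plan says.** Section 1.2 sets a secondary objective to be assessed with PRO-CTCAE "and a qualitative assessment, patient-reported side effects and acceptability of taking oral CBD (versus placebo"). Section 11 turns this into a planned output: "The side-effect profile, as measured by the PRO-CTCAE will be tabled according to side effect". Section 11.1 justifies the 2:1 allocation partly by better assessment of side effects.

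Section 5.1.3, headed "Instruments measuring study outcomes", has 8 entries, each with its timepoints. PRO-CTCAE is not one of them. The section 9 calendar has no PRO-CTCAE row either. For the post-dose visit, section 5.1.1 says only: "Timepoint 2 (Post-drug Administration): All participants will complete a set of questionnaires". It does not name them.

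The calendar row "Adverse Event Evaluation" is marked at Timepoint 1 and Timepoint 2 and is blank at Baseline and Timepoint 3. Timepoint 3 carries the qualitative telephone interview, a medical history entry and the gift card. Section 7.3.2 requires investigators to report adverse events up to 30 days after the dose. Section 5.6 sets follow-up of about one week.

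**The concern.** A secondary objective and a promised table rest on an instrument that the visit schedule does not provide for. The items, the recall period and the timing would have to be settled outside the protocol. If that happened late, or differed between participants, the table would be hard to interpret. If it did not happen, there would be no data to tabulate.

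The adverse-event row raises a related question. The protocol asks for reporting over 30 days, but the last marked evaluation comes no later than 4 h after a single dose. Effects that begin or persist after that would be recorded only if a participant volunteered them or an investigator came across them. Spontaneous reporting is a weak basis for comparing two arms, and the objective is framed against placebo.

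**Working it through.** The check sets the sections side by side. The only arithmetic concerns visit windows, and the plan gives no figure of its own to reproduce.

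**1. Measures named in section 1.2, traced to where they are scheduled.**

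| Measure | Section 5.1.3 | Section 9 calendar |
|---|---|---|
| PRO-CTCAE | absent | absent |
| Qualitative assessment | absent | Timepoint 3 |
| VAMS subscales | Timepoints 1, 2 | Timepoints 1, 2 |
| EORTC nausea items | Timepoints 1, 2 | Timepoints 1, 2 |
| NPRS | Baseline, Timepoints 1, 2 | Baseline, Timepoints 1, 2 |

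Of 5 measures, 3 are in both places and 1 is in the calendar only. PRO-CTCAE is the only one in neither.

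**2. The adverse-event row.** The pattern is blank, marked, marked, blank: 2 of 4 time points. The calendar footnote places dosing after the Timepoint 1 assessments, so that mark is pre-dose. Timepoint 2 is at 3 ± 1 h: 3 − 1 = 2 h to 3 + 1 = 4 h. One post-dose evaluation is therefore marked, at 2 to 4 h. A displaced table column is an unlikely explanation: the VAMS rows show the same pattern, and section 5.1.3 independently puts VAMS at Timepoints 1 and 2.

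**3. Marked evaluation against reporting duties.**
- Section 5.6: about 1 week of follow-up.
- Section 7.3.2: reporting to day 30.
- Timepoint 3: within a week, ± 7 days, so at the latest 7 + 7 = day 14. It has no adverse-event mark.
- Even after the latest Timepoint 3 call, 30 − 14 = 16 days of the reporting window have no scheduled contact.

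**4. What the other provisions supply.** CTCAE version 5.0 (section 7.2) is the system for adverse-event reporting and is distinct from PRO-CTCAE. Toxicity forms (7.6), evaluability for toxicity (11.7.1) and monitoring board review (10.2) set duties, but none schedules a question to the participant. VAMS Tired and the two EORTC nausea and vomiting items are asked at Timepoints 1 and 2. They are partial proxies for somnolence, which section 7.1.1 expects to be the leading adverse event, and for nausea and vomiting, but only up to 4 h.

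**5. What cannot be computed.** The documents give no single-dose event rate, so the number of events that might be missed cannot be estimated.

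**The case against.** Four points can fairly be made for the plan.

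- **Section 5.1.3 is not exhaustive.** It omits the qualitative interview, which is plainly planned. It also omits the drug-consumption query of section 8.1.9: "Patient drug accountability will be ensured through self-report in the form of query on Study Day Timepoint 2 (Appendix H"). Absence from the list alone therefore proves little. This stands. The weight rests on absence from the list and the calendar together, with no items, recall period or timepoints anywhere in the supplied text.
- **The form may exist.** The appendices were not supplied, and the questionnaires at Timepoints 1 and 2 may include PRO-CTCAE. The adverse-event row, with the same pattern as the patient-reported rows, may even be where it was meant to sit. This stands as a possibility. It would reduce the remedy to a citation, a proper label and a calendar row, but would not remove the need for them.
- **The calendar is incomplete elsewhere.** Its row "Confirmation of study drug consumption" is blank at every visit, although section 8.1.9 places that query at Timepoint 2. The blank Timepoint 3 cell in the adverse-event row therefore means unspecified, not excluded.
- **Later events have other routes.** The 30-day reporting rule, the week of follow-up, the Timepoint 3 interview and the Timepoint 3 record review may all bring them to light. This stands too, but none is a structured adverse-event question put to every participant.

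A reader might go further, and set the 2 to 4 h window against the stated time to peak concentration (2.5 to 5 h) or the 12 h driving restriction, to measure how much is missed. The documents do not support that. Section 2.2 gives the peak time at steady state, whereas this is a single dose, and nothing links the onset of adverse events to the peak or to the length of the driving precaution.

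**Conclusion.** The point holds as two specification gaps. First, PRO-CTCAE is the quantitative measure for a stated secondary objective and the source of a planned table, yet neither the instrument list nor the calendar provides for it. Second, adverse-event evaluation is marked once after dosing, at 2 to 4 h, and no structured question is scheduled later, despite the one-week and 30-day provisions.

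A reader might infer that PRO-CTCAE will not be collected, or that later adverse events will go unrecorded. Neither follows: an unsupplied form may exist, and the reporting duties remain in force. What follows is that the schedule as written does not collect the data for the table and does not systematically ascertain later side effects.

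The side-effect part of the 2:1 rationale is weakened, not nullified. Section 11.1 treats secondary analyses as exploratory, and the side-effect output is descriptive. The primary endpoint has its own scheduled assessments, so its analysis, power and alpha are untouched. The conclusion assumes that the supplied calendar was extracted correctly, as the VAMS cross-check suggests. The change should be made, but the primary inference does not depend on it.

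**What to change.** 1. Add PRO-CTCAE to section 5.1.3 with a fixed item set and a stated recall period. If a form already exists in an appendix, cite it there.
2. Give it a calendar row at Timepoint 1 (pre-dose), Timepoint 2 and the existing Timepoint 3 call. At Timepoint 3, state the recall period as since dosing, because the call can fall as late as day 14.
3. Mark adverse-event evaluation at Timepoint 3, using the same question for every participant. Reconcile the calendar row with sections 5.6 and 7.3.2, including how events after the last contact come to be known.
4. In section 11, state that each PRO-CTCAE item will be tabled descriptively by arm and timepoint, alongside its pre-dose level.

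This costs an amendment to section 5.1.3, section 11 and the calendar, with matching text in sections 5.6 and 7.3.2, plus a short added questionnaire at contacts that already exist. No extra visit is needed. The downside is some added burden on participants at those contacts.
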